## 7. Safety Evaluation Methods

### 7.1 Security Parameters

Vital signs, laboratory tests, adverse events occurring during clinical trials,

# 7.2 Description of Security Parameters

7.2.1 Vital Signs: Body temperature, respiration, heart rate, blood pressure;

Recording Time: Screening period, before surgery, during surgery, within 1 week after surgery ( $\leq 7$  days), 6 weeks after surgery  $\pm 1$  week, 12 weeks after surgery  $\pm 1$  week, 24 weeks after surgery  $\pm 4$  weeks, 48 weeks after surgery  $\pm 4$  weeks after surgery, 72 weeks after surgery  $\pm 4$ weeks.

7.2.2 Laboratory Examination: Coagulation function, blood routine, urine routine, blood biochemistry;

Recording Time: Screening period, within 1 week after surgery ( $\leq 7$ 

days), 24 weeks after surgery  $\pm$  4 weeks, 48 weeks after surgery  $\pm$  4 weeks after surgery, 72 weeks after surgery  $\pm$  4 weeks.

## 7.2.3 Adverse Events Occurred During Clinical Trials

Recording Time: Before surgery, 1 week after operation ( $\leq 7$  days), 6 weeks after surgery  $\pm$  1 week, 12 weeks after surgery  $\pm$  1 week, 24 weeks after surgery  $\pm$  4 weeks, 48 weeks after surgery  $\pm$  4 weeks after surgery, 72 weeks after surgery  $\pm$  4 weeks.

# **Trial Procedure**

#### 2.1 Screening Period (V0 period: -7-0 days)

Informed consent must be signed prior to any trial-related procedure, after which subjects are assigned a unique screening number that remains unchanged throughout the trial. If the subject is undergoing elective surgery, it is at the discretion of the investigator whether to re-examine the subject if the preoperative examination exceeds the acceptable time range.

(1) Sign informed consent;

(2) Demographic data: gender, age, height, weight;

(3) Complete medical history: previous disease history within 3 months before signing the informed consent, drug use history, smoking history, drinking history, surgical history and allergy history within 1 month;

(4) Vital signs: body temperature, respiration, heart rate, blood pressure;

(5) Blood pregnancy test: only applicable to women of childbearing age;

(6) Bone mineral density examination (test site);

(7) Blood glucose test: including blood glucose and glycated hemoglobin, only for diabetic patients;

(8) Coagulation function test: prothrombin time (PT), activated partial thromboplastin (APTT), fibrinogen (FIB), thrombin time (TT);

(9) Blood routine: hemoglobin (HB), red blood cell count (RBC), white blood cell count (WBC), platelet count (PLT), hematocrit (Hct);

(10) Urine routine: urinary white blood cells (WBC), urinary protein(PRO), urinary red blood cells (RBC), urinary glucose (GLU);

(11) Blood biochemistry: creatinine (Cr), Urea nitrogen (BUN) / Urea, alanine aminotransferase (ALT), aspartate aminotransferase (AST);

(12) C-reactive protein;

(13) Infectious disease examination: HBSAg, HBsAb, HBeAg, HBeAb,

HBcAb, HCV-rna/ HCV-antibody, syphilis TPPA, HIV antibody;

- (14) X-ray examination;
- (15) Determine the inclusion and exclusion criteria;
- (16) VAS score;
- (17) Recording device defects;
- (18) Record drug combination.

#### 2.2 Day of Surgery (Stage V1: Day 0)

- (1) Vital signs: body temperature, respiration, heart rate, blood pressure;
- (2) Random grouping;
- (3) Record surgical information;
- (4) Instrument performance index;
- (5) Recording device defects;
- (6) Record adverse events;
- (7) Records of combined drug use (except glucose, normal saline and

narcotic drugs);

#### 2.3 Follow-up Period (Phase V2: Within 1 week after surgery)

(1) Vital signs: body temperature, respiration, heart rate, blood pressure;

(2) Blood routine: hemoglobin (HB), red blood cell count (RBC), autologous cell count (WBC), platelet count (PLT), hematocrit (Hct);

(3) Urine routine: urinary white blood cells (WBC), urinary protein (PRO), urinary red blood cells (RBC), urinary glucose (GLU);

(4) Blood biochemistry: creatinine (Cr), Urea nitrogen (BUN) / Urea, alanine aminotransferase (ALT), aspartate aminotransferase (AST);

(5) X-ray examination;

(6) CT (3D reconstruction);

(7) MRI examination;

(8) VAS score;

(9) Recording device defects;

(10) Record adverse events;

(11) Record drug combinations (except glucose, normal saline and narcotic drugs);

### 2.4 Follow-up period (Stage V3: 6 weeks after surgery±1 week)

(1) Vital signs: body temperature, respiration, heart rate, blood pressure

(2) X-ray examination;

(3) Physical examination;

(4) Joint function score;

(5) VAS evaluation;

(6) Recording device defects;

(7) Record adverse events

(8) Record drug combinations (except glucose, normal saline and narcotic drugs)

#### 2.5 Follow-up Period (V4 period: 12 weeks after surgery±1 week)

(1) Vital signs: body temperature, respiration, heart rate, blood pressure;

(2) X-ray examination;

(3) Physical examination;

(4) Joint function score;

(5) VAS evaluation;

(6) Recording device defects;

(7) Record adverse events,

(8) Records of drug combinations (except glucose, normal saline and narcotic drugs)

## 2.6 Follow-up Period (V5: 24 weeks after surgery±4 weeks)

(1) Vital signs: body temperature, respiration, heart rate, blood pressure;

(2) Blood routine: hemoglobin (HB), red blood cell count (RBC), autologous cell count (WBC), platelet count (PLT), hematocrit (Hct)

(3) Urine routine: urinary white blood cells (WBC), urinary protein (PRO), urinary red blood cells (RBC), urinary glucose (GLU)

(4) Blood biochemistry: creatinine (Cr), Urea nitrogen (BUN) / Urea, alanine aminotransferase (ALT), aspartate aminotransferase (AST);

(5) X-ray examination;

(6) CT (3D reconstruction)

(7) MRI examination;

(8) Physical examination;

(9) Joint function score:

(10) VAS score;

(11) Recording device defects:

(12) Record adverse events;

(13) Record drug combinations (except glucose, normal saline and narcotic drugs)

#### 2.7 Follow-up Period (Phase V6: 48 weeks after surgery±4 weeks)

(1) Vital signs: body temperature, respiration, heart rate, blood pressure;

(2) Blood routine: hemoglobin (HB), red blood cell count (RBC), white blood cell count (WBC), platelet count (PLT), hematocrit (Hct);

(3) Urine routine: urinary white blood cells (WBC), urinary protein (PRO), urinary red blood cells (RBC), urinary glucose (GLU);

(4) Blood biochemistry: creatinine (Cr), Urea nitrogen (BUN) / Urea,

alanine aminotransferase (ALT), aspartate aminotransferase (AST);

(5) X-ray examination;

(6) MRI examination;

(7) Physical examination;

(8) Joint function score;

(9) VAS score;

(10) Recording device defects;

(11) Record adverse events;

(12) Record drug combinations (except glucose, normal saline and narcotic drugs);

#### 2.8 Follow-up Period (Stage V7: 72 weeks after surgery± 4 weeks)

(1) Vital signs: body temperature, respiration, heart rate, blood pressure;

(2) Blood routine: hemoglobin (HB), red blood cell count (RBC), white blood cell count (WBC), platelet count (PLT), hematocrit (Hct);

(3) Urine routine: urine white blood cell (WBC), urine egg (PRO), urine red blood cell (RBC), urine glucose (GLU);

(4) Blood biochemistry: creatinine (Cr), Urea nitrogen (BUN) / Urea, alanine aminotransferase (ALT), aspartate aminotransferase (AST);

(5) X-ray examination;

(6) MRI examination;

(7) Physical examination;

(8) Joint function score;

(9) VAS score;

(10) Recording device defects;

(11) Record adverse events;

(12) Record drug combinations (except glucose, normal saline and narcotic drugs);

# **Specifications for Use of Devices**

(1) All investigators performing the device operation in this clinical trial must be GCP certified, trained and skilled physicians.

(2) For unified handover of medical devices for testing, there should be a special person to check and process records. After the handover of the product, the medical device clinical trial management department.

(3) Each research unit shall establish a strict test instrument management system. For the special purpose of the device administrator form registration.

(4) The sponsor shall refer to the provisions of the State Drug Administration on the management of medical device instructions and labels, the experimental medical devices for appropriate identification, and marked "experimental".

(5) The records of experimental medical devices including production date, product batch number and other production-related records and product quality and stability related inspection records, Records of transportation and delivery of medical devices to clinical trial management departments for use, as well as post-trial recovery and disposal dates, etc.

(6) The use of investigational medical devices is the responsibility of the clinical trial institution and the investigator, and the investigator shall ensure that all investigational medical devices are used only for the subjects of the clinical trial, and the investigator shall not transfer the investigational medical devices to any non-participants in the clinical trial. Before use, sterilization should be carried out according to the requirements and instructions.

# **Statistical Analysis**

#### 1. Statistical Design

A prospective, multicenter, randomized, single-blind, parallel-controlled clinical trial was conducted. The comparison type was non-inferiority design.

#### 2. Analytical Methods

95% confidence interval method was used for the main efficacy indicators, and bilateral tests were used for all statistical tests, and P $\leq$ 0.05 was considered to be statistically significant.

The description of quantitative indicators will calculate the mean, standard deviation, median, minimum, maximum. The classification index is described by the number of cases and percentage of each type. Statistical analysis was performed using SAS 9.4 software.

# **Data Management**

#### (1) Data Recording and Transfer

**Electronic Case report Form (eCRF):** The data manager designed and constructed according to the experimental scheme, and set logical verification according to the data verification plan (DVP). After passing the test and obtaining the sponsor's approval, the ECRF will be released for use.

**Data entry:** The eCRF data comes from the original records, and the data entry personnel fill in the instructions according to the eCRF, and enter the subject's visit data into the EDC in time.

#### (2) Data Processing and Record Preservation

**Source data on-site verification (SDV):** The inspector can query the consistency of eCRF data and source data.

**Data questions and answers:** Questions come from EDC logical verification system questions, inspectors, data administrators and other manual questions, researchers need to answer questions in time. The data manager and the monitor give the question approval and issue the question again if necessary until the data is "cleared".

**Researcher signature:** After data entry is completed and passed through the SDV, the researcher will conduct an electronic signature review and confirmation.

If the data is modified after the signature, you need to re-sign it.

Adverse events were coded using the MedDRA (21.0 or above) dictionary, and drug combinations were classified by WHO ATC.

## (3) Database Locking

**Database locking:** After the principal investigator, sponsor, statistical analyst, and data manager jointly sign the database locking record, the data manager performs the database locking.

**Database submission:** Data manager submits database to statisticians, eCRF archive: eCRF generated PDF electronic document for each subject is saved, data management report: written by data manager,

**EDC shutdown:** After statistical analysis is complete, the data administrator closes the database.

# **Feasibility Analysis**

# (1) Analysis of the Possibility of Success

A. The test products have passed strict inspection, and the test results are qualified.

B. After training, the researchers are proficient in the use of the test equipment and operate in strict accordance with the plan.

C. Participants were selected according to strict inclusion/exclusion criteria.

#### (2) Possibility Analysis of Failure

This test routine does not fail, which may result in failure if :

A. Enrolled subjects who do not meet the inclusion criteria.

B. Failed to test relevant laboratory indicators according to the scheme.

C. The operator is not skilled in operation and makes mistakes in use.

# **Quality Control of Clinical Trials**

# (1) Training of Researchers

Before the start of clinical trial, the experimental institution or sponsor should conduct product training, program training and clinical trial process training according to the investigator's manual, specification and clinical protocol.

## (2) Measures to Improve Subjects' Compliance

Researchers should carefully implement informed consent so that subjects fully understand the requirements of the experiment and cooperate with the experiment.

#### (3) Supervision of Clinical trials

An auditor appointed by the sponsor conducts regular site visits to the trial hospital to ensure that all aspects of the study protocol are strictly adhered to and the CRF is checked to ensure consistency with the original data.

# Ethical Protection and Informed Consent in Clinical Trials

#### (I) Ethical Considerations

Clinical trials must be conducted in accordance with the Declaration of Helsinki and relevant clinical trial research norms and regulations in China. Before the start of the trial, the clinical trial can be carried out only after the trial protocol is approved by the ethics committee of the clinical trial unit.

Before each subject is enrolled in this study, it is the investigator's responsibility to provide him or his legal representative with a complete and comprehensive written description of the purpose, procedures, and possible risks of this study. Subjects should be made aware of their right to withdraw from the study at any time. A written informed consent must be given to each subject before enrollment, and the investigator is responsible for ensuring that each subject obtains informed consent before entering the study. Informed consent should be kept as clinical trial documentation for future reference.

#### (2) Informed Consent Process and Informed Consent

Before the participants participate in the clinical trial, the investigator shall fully explain the details of the clinical trial to the participants or their family members, guardians and legal representatives, including known and foreseeable risks and possible adverse events. After full and detailed explanation, the subject or his legal representative shall sign the name and date on the Informed consent, and the researcher performing the informed consent shall also sign the name and date on the informed consent, and the informed consent shall be signed before the subject accepts any test procedure, and any amendment shall be accompanied by a written explanation of the reason behind the Informed Consent.

The Informed consent should indicate the date of preparation or the date of the revised version. This information will help confirm that the correct version is being used. If the Informed Consent Form is revised during the experiment, the revised Informed Consent form shall be reviewed and approved by the Ethics Committee again before execution. After the revised Informed Consent is approved and sent to the clinical trial institution for record, all subjects who have not completed the trial process must sign the newly revised Informed Consent.

# Requirements for Reporting Adverse Events and Device Defects

#### (1) Definition and Reporting of Adverse Events

#### A. Definition of adverse events

Adverse events refer to adverse medical events that occur during clinical trials of medical devices, whether or not they are related to the experimental medical devices. Adverse events were recorded from device use.

#### **B.** Severity determination of adverse events

Observe the process, extent, disposal and outcome of adverse events in detail, and fill in the adverse event report form. Adverse events were classified as mild, moderate, and severely mild according to the following criteria:

Mild: Tolerable to the subject, does not affect treatment, does not require special treatment, and has no impact on the health of the subject

Moderate: The subject is unbearable, requires special treatment, has a direct impact on the health of the subject.

Severe: Endangering the life of the subject, causing death or disability, requiring immediate emergency treatment.

#### C. Evaluation of adverse events

According to the test product is definitely relevant, very likely to be relevant, possibly relevant, possibly irrelevant, definitely irrelevant five levels of evaluation.

Must be relevant: the occurrence of the reaction is consistent with a reasonable time sequence after the use of the product, consistent with the type of reaction known to the product, the disappearance of the reaction after discontinuation, and the reaction cannot be explained by clinical manifestations of the disease or other causes other than the product.

It is likely to be relevant: the occurrence of the reaction is consistent with a reasonable time sequence after the use of the product, consistent with the type of reaction known to the product, the reaction improves significantly after discontinuation, and the reaction cannot be explained by clinical manifestations of the disease or other causes other than the product.

May be relevant: The occurrence of the reaction is consistent with a reasonable time sequence after the use of the product, consistent with the type of reaction known to the product, the response improves after discontinuation, and the patient's clinical status or other treatment may cause a similar reaction.

May not be relevant: The occurrence of the reaction is not consistent with a reasonable time sequence after the use of the product, is not consistent with the type of reaction known to the product, the reaction improves after discontinuation, the patient's clinical status or other treatment may cause a similar reaction, and may be mitigated with disease improvement or other measures.

Certainly not: The occurrence of the reaction does not conform to a reasonable time sequence after the use of the product, does not conform to the type of reaction known to the product, the reaction does not improve after discontinuation, the patient's clinical status or other treatment may cause a similar reaction, the disease status improves or the response disappears after discontinuation of other treatment.

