# **4.5 Control Instrument Operation Methods**

The operation was carried out by professional doctors participating in this clinical trial according to the instructions.

Items	Experimental Device	Control Device
Name	Biologic Hollow Bone Screws	Inion Freedom Screws
Туре	SL30, SL32, SL34, SL36, SL38, SL40, SL42, SL44, SL46, SL48, SL50	Diameter :3.5mm/4.5mm Type: Hollow screw
Main Components	The product is made of silk fibroin protein, and the degradation products are amino acids and peptides, which are harmless to human body. The structure includes head thread, tail thread, rod part and hollow hole. The screw is a double-headed compression screw to achieve compression fixation at both ends of the fracture. It is hollow structure, which is not only easy to guide needle through, but also conducive to bone trabecular growth. Co60 irradiation	The product consists of an absorbable screw (L-lactic-D mixed with L-lactic acid copolymer) and a metal adapter (auxiliary screw screwing without contact with the human body). Made of 316 stainless steel according to ASTM F899 standard. Sterilized
	sterilization package.	

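### The causality scale for adverse events requires a response to discontinuation and a known reaction type, so reasonably timed reactions with the screw in place, or of a new type, fit no level

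*Protocol*

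**What the plan says.** The scale is in the protocol's adverse event chapter, part (1) C, Evaluation of adverse events. It has five levels, called here, in the plan's order, definite, probable, possible, unlikely and unrelated. There is no level for events that cannot be assessed, and neither the protocol nor the SAP gives another scale.

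- Definite requires reasonable timing, no other explanation, and a reaction "consistent with the type of reaction known to the product, the disappearance of the reaction after discontinuation".
- Probable has the same timing and type conditions, with "the reaction improves significantly after discontinuation, and the reaction cannot be explained by clinical manifestations of the disease".
- Possible again needs reasonable timing and a known type, with "the response improves after discontinuation, and the patient's clinical status or other treatment may cause a similar reaction".
- Unlikely needs timing and type that are "not consistent with a reasonable time sequence after the use of the product, is not consistent with the type of reaction known", and improvement after discontinuation.
- Unrelated also needs unreasonable timing, and a reaction that "does not conform to the type of reaction known to the product, the reaction does not improve after discontinuation".

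The products are implants. Protocol 4.3 has the screw fully seated in bone. In the 4.5 device table the test screw is silk fibroin, for which "the degradation products are amino acids and peptides"; for the control, "The product consists of an absorbable screw". Sections 4.1 and 4.4 mention removal only with mechanical failure or non-healing, and 4.5 adds nothing on removing the control. SAP 7C has the relationship recorded for each adverse event. Protocol section 2 states that investigators are not blinded.

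**The concern.** Discontinuation is a drug concept: treatment stops and one sees whether the reaction goes away. A screw that stays in bone and degrades there is not discontinued, and the protocol does not say what the word means for an implant. In the ordinary case the condition cannot be assessed, yet every level depends on it.

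The known-type condition is a second, separate obstacle. Protocol section 2 says that no screw of the same principle and material exists in China, so a reaction type not yet described for the product cannot be ruled out. A reasonably timed reaction of that kind is barred from the related levels by its type and from the unrelated levels by its timing.

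At stake is the usefulness of the recorded relationship ratings. Protocol 5.7 gives the tissue reaction to degradable implants as a reason for the long follow-up. Even if such reactions count as a known type, with the screw in place their rating depends on how each investigator at the six planned centres interprets a rule that does not fit.

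**Working it through.** The plan gives no figure to reproduce here. The check sets the five definitions side by side and tests each logical combination of their criteria.

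**1. The criteria as written**

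| Level | Timing reasonable | Type known | After discontinuation | Other explanation possible |
|---|---|---|---|---|
| Definite | yes | yes | disappears | no |
| Probable | yes | yes | improves significantly | no |
| Possible | yes | yes | improves | yes |
| Unlikely | no | no | improves | yes |
| Unrelated | no | no | does not improve | yes |

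The last two levels carry a further clause about mitigation or other treatment, which I take as met. It cannot affect steps 2 and 3, where both levels already fail on timing.

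**2. The combinations.** Timing (2) × type (2) × other explanation (2) × response (5: disappears, improves significantly, improves, does not improve, not assessable because the screw is in place) = 40.

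**3. The two gaps**

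- Reasonable timing, screw in place: 2 × 2 = 4 combinations. The first three levels fail on the response condition and the last two on timing. Result: 0 of 4. Counting a screw in place as no improvement does not help, because only the unrelated level uses that response and it needs unreasonable timing.
- Reasonable timing, new type: 5 × 2 = 10 combinations, 8 with the screw removed and 2 with it in place. The first three levels fail on type and the last two on timing. Result: 0 of 10.

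**4. Sensitivity to reading**

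- Strict reading, each response matching only its own wording: 5 of 40 combinations fit a level, one per table row.
- Inclusive reading, a stronger response also counting as a weaker one: disappearance and significant improvement now also satisfy the possible and unlikely levels, adding 2 + 2, so 5 + 4 = 9 of 40 fit. Both zeros in step 3 stand.
- Discontinuation clause ignored: delete the fourth column. Definite and probable then have identical rows (yes, yes, no). A reasonably timed reaction of a known type can be placed, but without another explanation it meets both of those levels. A reasonably timed reaction of a new type still fits none: 0 of 10.

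**The case against.** The strongest reply is that little depends on these ratings. Adverse events are recorded whether or not they are related. SAP 7C compares the incidence of adverse events and plans no comparison of related events. Serious events go to the sponsor, institution and ethics committee within 24 hours whatever their causality. Success is judged on the 24-week healing rate. All of this stands and sets the weight of the point.

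A second reply is that investigators will not apply the definitions as a strict checklist. They will choose the nearest level, so the practical result is inconsistent rating rather than unrated events. That is probably right, but it supports the change: the nearest level is undefined, and setting the discontinuation clause aside merges the top two levels and leaves new-type reactions unplaced.

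A third reply is that the protocol never defines a known reaction type and gives no closed list. Bending, loosening and breakage (4.1, 4.4) and tissue reaction (5.7) are already foreseen. This narrows the second gap to unforeseen reactions, whose frequency the documents do not let anyone estimate. It does not close the gap, and it does not touch the first.

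Two stronger readings are tempting. A reader might infer that unblinded rating biases the safety comparison between arms; the planned comparison does not use the ratings, and the documents support neither a size nor a direction for any difference. A reader might also infer that control-arm events go unrated, because the lead sentence begins "According to the test product is definitely relevant, very likely to be relevant" and SAP 7C refers to the experimental product. The level definitions say only the product, so this is a wording ambiguity and not an exclusion.

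**Conclusion.** The point holds as a defect in a stated rule. Read as joint conditions, the scale has no level for a reasonably timed reaction with the screw in place (0 of 4 combinations), nor for a reasonably timed reaction of a new type under any of the readings checked (0 of 10).

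The conclusion rests on three assumptions: that each level's conditions apply jointly (the natural reading, although the unrelated level is a comma list without a joining word); that discontinuation of an implant means its removal; and that screws normally stay in place, as sections 4.1, 4.3 and 4.4 imply. The counts describe the logic of the definitions and say nothing about how many events would be affected.

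The consequence is limited to the recorded relationship ratings. No event is lost, and no planned test or success criterion changes. It is a modest point that deserves correction because the change is cheap.

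**What to change.** Amend Evaluation of adverse events in the protocol:

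1. Apply the response-to-discontinuation criterion only if the implant was removed; otherwise mark it as not applicable.
2. Make a known reaction type supportive rather than required for the probable and possible levels.
3. Separate definite from probable by a criterion other than discontinuation, and assign events that still meet no level to a stated default level.

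Optionally, add a sentence there and in SAP 7C that the rating refers to the device implanted in either arm.

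I checked items 1 and 2 alone on the same combinations, inclusive reading. For reasonable timing with the screw in place, the number reaching a related level rises from 0 of 4 to 4 of 4, one of them meeting both definite and probable. For reasonable timing, new type and screw removed, it rises from 0 of 8 to 5 of 8: two probable (disappears or improves significantly, no other explanation) plus three possible (disappears, improves significantly or improves, with another explanation). Of the 4 badly timed combinations with the screw in place, 3 still fit no level. The double rating and these remaining gaps are why item 3 is needed.

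The cost is a short wording change in the protocol and eCRF, and one item in the investigator training already planned. The downside is that more events in both arms may be rated related.
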